7.3.1 SAE Reporting Requirements

- Participating investigators (all sites) must report all serious adverse events to the Lead Site Principal Investigator (e.g. Sponsor-Investigator) within **24 hours** of discovery or notification of the event. The participating investigator must also provide follow-up information on the SAE until final resolution.
 - Lead Site PI: [name], [contact] [contact].
Protocol coordinator can be contacted if applicable.
- The Lead Site Principal Investigator will review the SAE and report the event to IRB as applicable.
- It is the Principal Investigator's responsibility to ensure that ALL serious adverse events that occur on the study are reported to the Data Safety Toxicity Committee.

Institutional Review Board Reporting Requirements:

- Investigative sites will report adverse events to their respective IRB according to the local IRB's policies and procedures in reporting adverse events.

7.4 SAEs and OnCore

- All SAEs will be entered into OnCore.
- A copy of the SAE form(s) submitted to the sponsor-investigator is also uploaded into Oncore.

7.5 Data Safety and Toxicity Committee

It is the responsibility of each site PI to ensure that ALL SAEs occurring on this trial (internal or external) are reported to the Case Comprehensive Cancer Center's Data and Safety Toxicity Committee. This submission is simultaneous with their submission to the sponsor and/or other regulatory bodies.

The sponsor-investigator is responsible for submitting an annual report to the DSTC as per CCCC Data and Safety Monitoring Plan.

7.6 Data and Safety Monitoring Plan (DSMP)

This protocol will adhere to the policies of the Case Comprehensive Cancer Center Data and Safety Monitoring Plan in accordance with NCI guidelines.

8.0 EXPLORATORY ENDPOINTS

8.1 Dosimetric Comparison of TFRT and Conventional IMRT

Dosimetric parameters including the mean dose, maximum dose, and minimum dose to the organs at risk will be analyzed among the subplans, composite TFRT plan, and conventional IMRT plan.

8.1.1 Background

Using the dynamic NTCP model, the greatest difference between d_H and d_L theoretically will create the biggest reduction in normal tissue complication probability. To further

understand the appropriate prioritization parameters dosimetric endpoints will be compared.

8.1.2 Rationale for Analysis

The dosimetric parameters will be reported in a descriptive pattern to detail the planning parameters used to optimize temporally feathered radiation therapy plans.

9.0 STUDY PARAMETERS AND CALENDAR

9.1 Study Parameters

9.1.1 Screening Evaluation

Evaluations including that needed to establish diagnosis, will be used to determine the eligibility of each subject for study inclusion. All evaluations must be completed < 40 days prior to administration of protocol therapy.

9.1.2 Treatment Period

Patients will be evaluated in consultation, at which time information will be gathered regarding trial eligibility. Subsequently, patients will undergo CT simulation, initiation of radiation delivery, and weekly on-treatment visits. Follow-up visits will occur 2 weeks, 4 weeks, and 3 months post completion of treatment. At the indicated visits below, toxicity will be assessed by way of CTCAE criteria and patient-reported quality of life questionnaires.

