The biologic basis of dose and fractionation arises from the four pillars of radiobiology: (i) repair of sub-lethal damage, (ii) reassortment of cells within the cell cycle, (iii) repopulation, and (iv) reoxygenation.¹⁰ Recovery from radiation-induced toxicity is primarily dependent on sub-lethal damage repair and repopulation. For this reason, fractionated radiotherapy still predominates in the clinic. As a low fractional dose of radiation is delivered daily, consistent insult is delivered to tumor cells while allowing time for normal tissue recovery between fractions. Despite this, as discussed above, toxicity still manifests mid-way or toward the end of most treatment courses acutely and late toxicities remain dose-limiting. Attention has been turned to techniques to widen the therapeutic ratio between tumor control probability (TCP) and normal tissue complication probability (NTCP). This had been achieved previously by pharmaceuticals such as radiosensitizers and radioprotectants, until the advent of intensity modulated radiation therapy (IMRT), which now is one of the greatest contributors to reduced toxicity associated with radiotherapy.^{2,11,12} The implementation of IMRT into clinical practice

took nearly 50 years from when [name] solved the inverse problem of IMRT in the 1940s, until [name] illustrated the IMRT principles in 1988, and ultimately when the Peacock planning system was used to treat the first patient with IMRT in the mid-1990s.¹³⁻¹⁷

As an extension of IMRT, other researchers namely [name] have examined the role of altering both the fractional dose delivered to the target as well as the organs at risk to continue to widen the therapeutic ratio.¹⁸⁻²² Temporally feathered radiation therapy takes a different approach to reducing toxicity, without altering target volume coverage or dosing. Temporally feathered radiation therapy optimizes not only the physical distributions of dose, but also the time through which radiation therapy is delivered with the goal of allowing increased time for normal tissue recovery between fractional doses. Preclinical data demonstrating the potential benefit of TFRT are discussed below (section 1.2.1).²³

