6.2 Dose Specifications

6.2.1 Dose Fractionation

Patients must be eligible to receive 70 Gy in 35 fractions to the primary target (PTV_7000) and to receive 56 Gy in 35 fractions to the elective volume (PTV_5600). The doses are prescribed at the edge of the PTV. Treatment will be delivered once daily from Monday to Friday over 7 weeks. Missed treatments can be compensated for by treating on the Saturday or Sunday of that week, or adding to the end of treatment.

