9.2 Calendar

At the scheduled visits below the patients will undergo evaluation of toxicity with physician-assigned grade as per CTCAE V4 as well as patient reported outcome measures using EORTC QLQ-C30, EORTC QLQ-HN35 and Xerostomia Questionnaire (XQ) as demonstrated in Appendix IV.

A visit window of +- 4 days is allowed for the visits while the patient is undergoing treatment. A visit window of +- 7 days is allowed for the visits 2 and 4 weeks after completing treatment. A visit window of +- 28 days is allowed for the 3 month post-treatment.

Study Days	Wk 1 of RT (+- 4 days)	Wk 4 of RT (+- 4 days)	Wk 7 of RT (+- 4 days)	2 Wks post- RT (+- 7 days)	4 wks post RT (+- 7 days)	3 mos post RT (+- 28 days)
REQUIRED ASSESSMENTS						
Weight	X	X	X	X	X	X
Vitals (blood pressure, pulse, respiratory rate, and temperature)	X	X	X	X	X	X
Physical Examination	X	X	X	X	X	X
Adverse Event Assessment	X	X	X	X	X	X
PRO Assessment	X	X	X	X	X	X

Karnofsky PS	X	X	X	X	X	X
--------------	---	---	---	---	---	---

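### CTCAE grading is scheduled in only three of the seven treatment weeks although patients are seen weekly, so acute grade 3-5 toxicity may be under-ascertained; a cheap, low-priority fix is available

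*Combined protocol and SAP*

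**What the plan says.** Section 9.1.2 states that "patients will undergo CT simulation, initiation of radiation delivery, and weekly on-treatment visits". It then limits toxicity assessment to the visits listed after it: "At the indicated visits below, toxicity will be assessed by way of CTCAE criteria and patient-reported quality of life questionnaires". Section 9.2 repeats the link: "At the scheduled visits below the patients will undergo evaluation of toxicity with physician-assigned grade as per CTCAE V4".

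The calendar row "Adverse Event Assessment" is marked in six columns: weeks 1, 4 and 7 of radiotherapy, then 2 weeks, 4 weeks and 3 months afterwards. There is no column for weeks 2, 3, 5 or 6. On timing, "A visit window of +- 4 days is allowed for the visits while the patient is undergoing treatment".

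Section 1.1 says that "toxicity still manifests mid-way or toward the end of most treatment courses acutely". Sections 2.2 and 11.0 make acute grade 3-5 toxicity the first secondary endpoint; Section 2.2 sets its limit at 90 days after radiotherapy.

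Adverse events are also captured outside the calendar. Section 7.1.3 requires every event that staff notice or the patient raises after consent to be recorded, with CTCAE term, grade, attribution, and onset and resolution dates. It sends related non-serious events and all serious events to the database. Section 7.3 covers the period from registration to 90 days after the course. The note that opens Section 7.0, however, limits reporting to serious adverse events.

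**The concern.** The patient is in clinic every week, yet in four of the seven treatment weeks no toxicity grade is scheduled. The longest on-treatment interval without one can fall in the second half of the course, where the protocol itself expects acute toxicity to appear.

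What is at stake is how completely the grade 3-5 endpoint is ascertained. An event that is serious but brief is likely to be captured through SAE reporting. The vulnerable case is a grade 3 event that does not meet the seriousness criteria and that begins and improves between two graded visits. It enters the estimate only if someone notes it, grades it and reports it. The last step depends on whether a site follows 7.0 or 7.1.3. Any error of this kind lowers the estimate. Section 1.2.2 says that no clinical data on TFRT exist, so these would be the first toxicity figures for the technique.

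**Working it through.** The documents state no maximum interval between grades, so there is no plan figure to reproduce. The check is calendar arithmetic followed by a comparison of the reporting rules.

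**Inputs**
- Weekly on-treatment visits (9.1.2); grading in weeks 1, 4 and 7 (9.2).
- Window of 4 days either way on treatment (9.2).
- After treatment: "A visit window of +- 7 days is allowed for the visits 2 and 4 weeks after completing treatment".
- Fractionation (6.2.1): "Treatment will be delivered once daily from Monday to Friday over 7 weeks", 35 fractions in all.
- Assumptions: day 1 is the Monday of week 1, no fractions are missed, and visits fall on the same weekday. The last fraction is then on day 6 × 7 + 5 = 47.

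**1. Treatment weeks without a scheduled grade.** 7 − 3 = 4 (weeks 2, 3, 5 and 6).

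**2. Nominal gap** = 7 × (later week − earlier week).
- Weeks 1 to 4: 7 × 3 = 21 days.
- Weeks 4 to 7: 7 × 3 = 21 days.

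**3. Range with the windows.** Maximum 21 + 4 + 4 = 29 days; minimum 21 − 4 − 4 = 13 days.

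**4. Where the 29 days can fall.**
- With Monday visits, week 4 is day 22 and, taken 4 days early, day 18. By then 5 + 5 + 4 = 14 of the 35 fractions have been given.
- Week 7 is day 43 and, taken 4 days late, day 47, the day of the last fraction. The gap is 47 − 18 = 29 days, all within treatment.
- For weeks 1 to 4 with Monday visits, the first visit cannot precede day 1 if it is to be on treatment, so the maximum is 22 + 4 − 1 = 25 days. The full 29 days needs Friday visits (day 5 − 4 = 1 to day 26 + 4 = 30).
- If a calendar week means any treatment weekday and the window is added to that, the maximum for weeks 4 to 7 is (47 + 4) − (22 − 4) = 33 days. The 29-day figure is therefore not the most extreme reading.

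**5. With grading at every weekly visit.** Nominal gap 7 days; maximum 7 + 4 + 4 = 15 days if the same window applies.

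**6. Week 7 to the 2-week follow-up visit.** Earliest week 7 visit: 43 − 4 = day 39. Latest follow-up visit: 47 + 14 + 7 = day 68. Maximum gap 68 − 39 = 29 days. Weekly grading changes neither end of this interval.

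**7. What the event-driven rules add.** Section 7.1.3 covers an event that is noticed at, say, a week 5 visit: it must be recorded with a grade and dates. Section 7.3 confirms the period. Neither sets a time at which toxicity must be looked for. Read against 7.0, a non-serious grade 3 mucositis attributed to radiotherapy goes to the database under 7.1.3 but is not reported under 7.0. The two cannot both be followed for such an event.

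**8. Weight of one event.** With five patients, one patient missed moves the proportion by 1/5 = 20 percentage points.

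**The case against.** The strongest answer is that adverse events are recorded anyway. A clinician sees the patient each week, and 7.1.3 obliges the team to record and grade what is observed, with onset and resolution dates. The amendment log shows that 7.1.3 was revised specifically to clarify what enters the database. This stands as real mitigation: the protocol does not leave the intervening weeks unrecorded. What it lacks is a scheduled prompt, and the conflicting note in 7.0 remains in the text.

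A reader might go further and infer that anything confined to a gap is lost. If grading captured only status on the visit day, an episode of D days starting at random in a 21-day gap would be missed with probability (21 − D)/21: 67% for 7 days and 33% for 14 days. The documents do not support using these figures. The recording duty in 7.1.3 contradicts the assumption, and neither duration has a source in the protocol. The one duration given, in Section 1.1, is a median of 1.7 months of acute feeding tube use among patients who needed one. That is longer than 29 days, so an episode of that length could not fall inside a gap. It does not represent every toxicity.

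A reader might also infer that weekly grading would catch every episode of 7 days or more. With the windows, weekly visits can still be 15 days apart, so that does not follow.

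Finally, the endpoint is secondary and descriptive, and no feasibility decision, comparison or stopping rule uses it. Section 1.3 leaves powered toxicity outcomes to later studies. Two events in five patients would have an exact 95% interval of about 5% to 85%, so precision is poor whatever the schedule. This stands, and it limits the priority of the point.

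**Conclusion.** The point holds as a gap in systematic ascertainment, not as a failure to capture events. Scheduled CTCAE grades during radiotherapy are nominally 21 days apart and can be 29 days apart, in the period in which the protocol expects toxicity. The 29 days rests on same-weekday visits, full use of both windows and, for it to lie wholly within treatment in weeks 4 to 7, Monday visits with no missed fractions.

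Between those visits the endpoint depends on event-driven recording without set assessment times, under reporting rules that disagree between 7.0 and 7.1.3. Non-serious grade 3 events may therefore be under-ascertained and the acute grade 3-5 estimate may be biased low. The documents give no basis for saying by how much.

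This is a low-priority, cheap improvement. The primary feasibility endpoint, start of radiotherapy within 15 days of simulation, is unaffected.

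**What to change.** - In the 9.2 calendar, mark the adverse event assessment with CTCAE grade at each weekly on-treatment visit, weeks 1 to 7. Leave the patient-reported outcome schedule as it is.
- In Section 11.0, state that acute toxicity is reported as the worst grade per patient from the start of radiotherapy through 90 days after it, using scheduled grades plus events recorded under 7.1.3.
- Reconcile the note in 7.0 with 7.1.3, so that it is clear which non-serious events reach the database.

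The nominal on-treatment gap falls from 21 to 7 days and the maximum from 29 to 15. The interval from week 7 to the 2-week follow-up visit does not change.

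Cost: four more CTCAE entries per patient, 4 × 5 = 20 in total, at visits that already take place, plus the text edits. No added visits, staff or procedures.

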9.2 Calendar

At the scheduled visits below the patients will undergo evaluation of toxicity with physician-assigned grade as per CTCAE V4 as well as patient reported outcome measures using EORTC QLQ-C30, EORTC QLQ-HN35 and Xerostomia Questionnaire (XQ) as demonstrated in Appendix IV.

A visit window of +- 4 days is allowed for the visits while the patient is undergoing treatment. A visit window of +- 7 days is allowed for the visits 2 and 4 weeks after completing treatment. A visit window of +- 28 days is allowed for the 3 month post-treatment.

Study Days	Wk 1 of RT (+- 4 days)	Wk 4 of RT (+- 4 days)	Wk 7 of RT (+- 4 days)	2 Wks post- RT (+- 7 days)	4 wks post RT (+- 7 days)	3 mos post RT (+- 28 days)
REQUIRED ASSESSMENTS						
Weight	X	X	X	X	X	X
Vitals (blood pressure, pulse, respiratory rate, and temperature)	X	X	X	X	X	X
Physical Examination	X	X	X	X	X	X
Adverse Event Assessment	X	X	X	X	X	X
PRO Assessment	X	X	X	X	X	X

Karnofsky PS	X	X	X	X	X	X
--------------	---	---	---	---	---	---

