2.2 Secondary Objective(s)

- (1) Estimate grade 3-5 acute toxicity (within 90 days after RT)
- (2) Patient-reported outcomes (PRO) of toxicity during and after TFRT.
- (3) Compliance with plan delivery

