6.12 Duration of Follow Up

Subjects will be followed for toxicity for 3 months after treatment has been completed/discontinued or until death, whichever occurs first.

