7.1.3 Adverse Event Evaluation

The investigator or designee is responsible for ensuring that all adverse events (both serious and non-serious) observed by the clinical team or reported by the subject which occur after the subject has signed the informed consent are fully recorded in the subject's medical records. Source documentation must be available to support all adverse events.

For the purposes of data collection, only non-serious adverse events that are possibly, probably or definitely related to protocol treatment will be reported in the database. Serious adverse events of any attribution will be reported in the database.

A laboratory test abnormality considered clinically relevant (e.g., causing the subject to withdraw from the study, requiring treatment or causing apparent clinical manifestations, result in a delay or dose modification of study treatment, or judged relevant by the investigator), should be reported as an adverse event.

The investigator or sub-investigator (treating physician if applicable) will provide the following for all adverse events (both serious and non-serious):

- Event term (as per CTCAE)
- Description of the event
- Date of onset and resolution
- **Expectedness of the toxicity**
- **Grade of toxicity**
- **Attribution of relatedness to the treatment- (this must be assigned by an investigator, sub-investigator, or treating physician)**
- Action taken as a result of the event, including but not limited to; no changes,

- dose interrupted, reduced, discontinued, etc. or action taken with regard to the event
- Outcome of event

Descriptions and **grading scales** found in the NCI Common Terminology Criteria for Adverse Events (CTCAE) version 4.0 will be utilized for AE reporting.

An expected adverse event is an event previously known or anticipated to result from participation in the research study or any underlying disease, disorder, or condition of the subject. The event is usually listed in the Investigator Brochure, consent form or research protocol.

An unexpected adverse event is an adverse event not previously known or anticipated to result from the research study or any underlying disease, disorder, or condition of the subject.

Attribution is the relationship between an adverse event or serious adverse event and the prescribed course of radiotherapy. Attribution will be assigned as follows:

- Definite – The AE is clearly related to the prescribed course of radiotherapy.

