7.3 Reporting Procedures for Serious Adverse Events

For the purposes of safety reporting, all adverse events will be reported that occur from the day of registration through 90 days after the completion of the prescribed course of therapy. Adverse events, both serious and non-serious, and deaths that occur during this period will be recorded in the source documents. All SAEs should be monitored until they are resolved or are clearly determined to be due to a subject's stable or chronic condition or intercurrent illness(es). Related AEs will be followed until resolution to baseline or grade 1 or stabilization.

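### The ±28-day window lets the last scheduled toxicity grading fall at about day 62-64 after radiotherapy, although the toxicity endpoint runs to day 90

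*Combined protocol and SAP*

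**What the plan says.** Section 2.2 lists the first secondary objective as "Estimate grade 3-5 acute toxicity (within 90 days after RT"; the Protocol Summary gives the same 90-day limit. Section 11.0 repeats the endpoint as acute grade 3-5 toxicity by CTCAE version 4, with no time window.

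The visits are set in Section 9.1.2: "Follow-up visits will occur 2 weeks, 4 weeks, and 3 months post completion of treatment". The calendar in Section 9.2 requires adverse event assessment in weeks 1, 4 and 7 of treatment and at the three post-treatment visits. Nothing is scheduled after the 3-month visit. For the first two post-treatment visits, "A visit window of +- 7 days is allowed for the visits 2 and 4 weeks after completing treatment". For the last, "A visit window of +- 28 days is allowed for the 3 month post-treatment".

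Three other provisions bear on the point. Section 7.3 sets the period for reporting adverse events by date, not by visit: "from the day of registration through 90 days after the completion of the prescribed course of therapy". Section 6.12 says: "Subjects will be followed for toxicity for 3 months after treatment has been completed/discontinued or until death, whichever occurs first". Section 7.1.3 lists "Date of onset and resolution" among the items to be recorded for every adverse event.

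**The concern.** An endpoint that runs to day 90 needs some planned look at the patient on or after day 90. The window around the 3-month visit is symmetric, so that visit can take place almost four weeks before the endpoint period ends, and no later one follows. Two patients who both comply with the calendar can then have their last physician grading about eight weeks apart.

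At stake is the completeness of the grade 3-5 estimate. For a patient seen early, an event after the visit reaches the record only if someone happens to report it. A missed event lowers the estimate if that patient had no other qualifying event, and with five patients one such misclassification moves the proportion by 1/5 = 20 percentage points. Section 1.3 says that later studies will be powered for toxicity, so a clearly bounded estimate is worth having even though nothing is tested here.

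There is also a smaller matter at the other end. The endpoint wording names the days after radiotherapy and does not say whether the treatment weeks count.

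**Working it through.** The plan gives no figure of its own to reproduce on this point. The check is date arithmetic, counting days from the end of radiotherapy.

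**Inputs**
- Endpoint limit: day 90 (Section 2.2).
- Window for the last visit: ±28 days (Section 9.2).
- Window for the 4-week visit: ±7 days (Section 9.2), so days 21 to 35.
- Treatment: 7 weeks, Monday to Friday (Section 6.2.1). For a Monday start with no missed fractions, first to last fraction spans 6 × 7 + 5 = 47 calendar days.
- Length of 3 months: not defined in the plan. Assumption: 90 to 92 days, with 84 days (12 weeks) as a sensitivity case.

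**1. Earliest last visit and what follows it**

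Earliest day = (3 months in days) - 28. Days without scheduled grading = 90 - earliest day.

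| 3 months taken as | Earliest day | Days left to day 90 | Share of 90 days | Share of 47 + 90 = 137 days |
|---|---|---|---|---|
| 90 days | 62 | 28 | 31.1% | 20.4% |
| 91 days | 63 | 27 | 30.0% | 19.7% |
| 92 days | 64 | 26 | 28.9% | 19.0% |
| 84 days | 56 | 34 | 37.8% | 24.8% |

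**2. Latest last visit**

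Latest day = (3 months in days) + 28, which gives day 118 to 120 (day 112 for 84 days). Events after day 90 can be found at a late visit, but the onset dates required by Section 7.1.3 allow them to be left out.

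**3. Gap after the 4-week visit (3 months = 91 days)**

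- Longest gap now: 119 - 21 = 98 days.
- Shortest gap now: 63 - 35 = 28 days.
- With the last visit no earlier than day 90, the shortest gap becomes 90 - 35 = 55 days. The longest stays at about 98 days (97 if the window is counted from day 90, since 118 - 21 = 97).

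**4. Start of the window**

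Section 2.2 names no start. Section 7.3 collects events from registration, and the calendar requires assessments in weeks 1, 4 and 7 of treatment. The treatment-period data will therefore exist. What is missing is a statement that they belong to the endpoint.

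**The case against.** The strongest reply is that ascertainment does not depend on the visit. Section 7.3 makes adverse events reportable through day 90, Section 6.12 follows toxicity for 3 months, and Section 7.1.3 requires events seen by the team or reported by the patient to be recorded. This stands against a reading that is easy to fall into: a reader might infer that the endpoint is closed at about day 63 and the rest of its window goes unobserved. The documents do not support that, since no section ends ascertainment at the last visit. What remains is narrower. Section 7.3 sets the obligation, but no section names a visit, call or record check that would meet it after an early last visit.

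A second reply is that share of days is not share of risk. Section 1.1 describes acute toxicity as appearing from about the middle of a course onward or near its end. The estimate changes only if a patient's first grade 3-5 event arises after an early last visit and also goes unreported. The documents give no rate for this. The reply stands, and it is why the likely effect is small.

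A third is that the endpoint is secondary and descriptive, in a single-arm study of five patients, with no comparison of toxicity planned. That also stands and limits the weight of the point.

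Finally, a reader might infer from the endpoint wording that toxicity during treatment is not captured. It is captured, as the working shows. Only the label is incomplete.

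**Conclusion.** The point holds as a minor one. The calendar and the endpoint period do not match: a compliant patient can have 26 to 28 of the 90 post-radiotherapy days, roughly 30%, with no scheduled CTCAE grading. Counting the 47 treatment days, the share is about 20%. These figures assume 3 months of 90 to 92 days and a last visit at the early edge of its window. Thirty percent is not a strict upper limit, because a 12-week reading gives 37.8%.

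The direction of any bias is clear, since a missed event can only lower the grade 3-5 proportion. Its size cannot be computed from the documents and is probably small. The primary endpoint, starting radiotherapy within 15 days of simulation, is not affected.

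**What to change.** In Section 9.2, set the last toxicity assessment no earlier than day 90 after radiotherapy, for example -0/+28 days. State day 90 explicitly, because 3 months is not defined in days. For the endpoint, count only events with onset through day 90, using the onset dates that Section 7.1.3 already requires.

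As a minor clarification, state in Sections 2.2 and 11.0 that the endpoint is the worst CTCAE grade with onset from the first fraction through day 90 after the last fraction.

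The cost is wording, with no added visit. The site loses the option of booking the last visit early, and the average interval after the 4-week visit becomes longer, with a correspondingly longer recall period. The longest gap, about 98 days, is essentially unchanged, so this change does not address it.
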